### **Longitudinal Validation Power and Sample Size**

An empirical power analysis simulation was conducted to evaluate the optimal sample size to adequately characterize culture converter anchor-based within-subject meaningful change in this study.

Inputs to the power analysis simulations were obtained from the MAC subset of the ALIS treated subjects in Insmmed Study TR02-112, and simulation conditions considered reflected conservative variation around observed estimates (larger dispersion and smaller magnitudes of effect). The following conditions were used to compute power: magnitudes of effect in change from baseline (6pt, 7pt, 8pt, 9pt, and 12pt change from baseline in converters, and 3 point change from baseline in non-converters); culture converter proportions (50%, 60%, and 70%); proportion data missing at random (MAR, 0%, 5%, 20%, 25%, and 30%); and sample size (n=100, n=120, and n=130). The polyserial correlation between simulated change from baseline in QOL-B respiratory domain and culture conversion varied around the observed estimate of 0.47, ranging from 0.3 to 0.6. Within each unique simulation condition r=1000 replications were generated. Empirical power was computed as the number of replications for which statistically significant differences between converters and non-converters in change from baseline in QOL-B respiratory domain score were observed. For example, if 900 replications demonstrated significant differences using the 2-sided test conducted at  $\alpha=0.05$ , then power was 90%.

A total sample size of 100 subjects (50 subjects per treatment arm) will provide at least 80% power for detecting 7 points mean difference in QOL-B respiratory domain response at 1-month post-treatment between subjects achieving culture conversion during the study and those who did not via ANOVA testing. This derivation assumes 50%, 60%, or 70% culture conversion rate, at least 40% polyserial correlation between culture conversion and QOL-B respiratory domain response, and missing data of 0%, 5%, or 20%.

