#### **9.3.2.2. Analysis**

The analysis of change from baseline to Month 7 in respiratory symptom score (as assessed by QOL-B) will be summarized based on subjects in the ITT analysis set by treatment group.

The analysis model is the ANCOVA, the model includes response variable, ie, change from baseline to Month 7 and the following independent variables:

- history of MAC lung infection, (initial or subsequent)

- baseline QOL-B Respiratory domain score

The regression coefficient for treatment group in the ANCOVA is equal to the estimated population-level average treatment effect of  $\mu_{\text{ALIS}} - \mu_{\text{ELC}}$ ; this estimate will be used in Wald tests deriving p-value for the difference between the treatment groups. The p-value is nominal as the study is not a hypothesis testing and further is not powered for this comparison.

The summaries will include:

1. LS-mean of change from baseline to Month 7, differences of LS-mean changes from baseline (ALIS + background regimen minus ELC + background regimen) estimates and corresponding 95% CIs derived from ANCOVA model.
2. Descriptive statistics by timepoint with corresponding change from baseline.

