## 11.4. Correlations

Correlations between QOL-B (Respiratory Symptoms Domain), PROMIS F-SF 7a (raw score) (denoted 'PROs' below) and microbiology variables will be investigated. Missing data for this analysis will not be multiply imputed, however all other rules described in [Sections 9.3.1.2](#) and [9.3.2.2](#) that allow deterministically assign missing values will be applied.

- Change from baseline to Month 6 in PROs vs Culture conversion by Month 6
- Change from baseline to Month 7 in PROs vs Culture conversion by Month 6

- Change from baseline to Month 6 in PROs vs Culture conversion by Month 7
- Change from baseline to Month 7 in PROs vs Culture conversion by Month 7

Correlations will be evaluated by treatment group and for overall using point biserial correlation and ANOVA/ANCOVA with response variable of change from baseline in PRO, and independent variables culture conversion status, and treatment (if appropriate). Basic statistics of change from baseline in PRO scores by converter status will also be provided.

In addition, plots of change from baseline PRO mean scores over time will be presented for converters and non-converters.

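### The SAP 11.4 model of PRO change by culture conversion status does not list the baseline PRO score, although converters and non-converters are not randomised groups

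*SAP*

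**What the plan says.** SAP 11.4 examines change in the QOL-B respiratory score and the PROMIS fatigue raw score against culture conversion. There are four pairings: change to Month 6 or Month 7, with conversion by Month 6 or by Month 7. Each is evaluated by arm and overall, using a point-biserial correlation and "ANOVA/ANCOVA with response variable of change from baseline in PRO, and independent variables culture conversion status, and treatment (if appropriate". Both listed predictors are categorical.

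Elsewhere the SAP adjusts PRO change for baseline. The ANCOVA in 9.3.2.2 lists "baseline QOL-B Respiratory domain score", and those in 10.2.2 and 11.1.5 include the baseline value.

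Two other parts of the documents set the context:
- SAP 4.3.1, with matching text in Protocol 10.1, says that 100 subjects "will provide at least 80% power for detecting 7 points mean difference in QOL-B respiratory domain response at 1-month post-treatment". The groups compared, and the test, are then given as "between subjects achieving culture conversion during the study and those who did not via ANOVA testing".
- SAP 2, 3.1 and 5.1 assign the psychometric validation, including within-subject meaningful change, to the Validation Analysis Plan (VAP). SAP 7.2 makes all SAP summaries descriptive, with nominal p-values.

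**The concern.** Where the SAP compares randomised arms, baseline adjustment mainly buys precision, and the SAP uses it. In 11.4 the groups are defined by an outcome that arises after randomisation, so nothing protects baseline balance, yet the baseline score is not listed.

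There are design reasons to expect change to depend on baseline. Entry requires an average QOL-B respiratory score of 85 or less, and that average includes the enrolment-day score (Protocol 4.1.1). Selecting on the score later used as baseline invites regression to the mean. The 0 to 100 scale also limits how far high scorers can improve.

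Baseline symptoms could also be linked to conversion status. Before conversion, a non-productive visit counts as culture positive (SAP 9.3.1.1), and bringing up mucus is one of the respiratory items. The direction of any imbalance cannot be told from the documents.

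At stake is how the SAP's description of symptom change in converters and non-converters is read. A baseline difference could make the association look larger or smaller than it would among subjects who started at the same level.

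**Working it through.** **1. The plan's own power figure.** Inputs from SAP 4.3.1: N = 100, two-sided alpha 0.05, a 7-point difference, 50%, 60% or 70% converters (p), polyserial correlation of at least 0.40, and 0%, 5% or 20% missing. No SD is given, so it is derived from the correlation:

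- point-biserial r = 0.40 × φ(z_p) / √(p(1−p)) = 0.319, 0.315, 0.303 for p = 0.5, 0.6, 0.7
- within-group SD = 7 × √(p(1−p)) / r × √(1−r²) = 10.39, 10.32, 10.07

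Noncentral-t power with no baseline covariate:

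| Converters | 0% missing | 5% missing | 20% missing |
|---|---|---|---|
| 50% | 0.915 | 0.901 | 0.845 |
| 60% | 0.908 | 0.894 | 0.836 |
| 70% | 0.884 | 0.867 | 0.803 |

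A simulation from a latent bivariate normal gives 0.795 in the lowest cell. The stated figure of at least 80% therefore reproduces, to within simulation and approximation error, for an unadjusted ANOVA. The SE of the contrast runs from about 2.1 points (50% converters, N = 100) to 2.5 points (70% converters, N = 80).

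**2. Effect of adding baseline.** The baseline to follow-up correlation ρ is not in the documents. Assume ρ = 0.4 to 0.7 and equal SDs s at both times, within groups:

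- variance of change = 2(1−ρ)s²
- variance of change given baseline = (1−ρ²)s²
- ratio = (1+ρ)/2
- slope of change on baseline = −(1−ρ), so a baseline difference d moves the unadjusted contrast by (1−ρ)d relative to the adjusted one, in the direction opposite to d

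| ρ | Variance ratio | Fall in SE | Shift, d = 5 | Shift, d = 2 |
|---|---|---|---|---|
| 0.4 | 0.70 | 16% | 3.0 | 1.2 |
| 0.5 | 0.75 | 13% | 2.5 | 1.0 |
| 0.6 | 0.80 | 11% | 2.0 | 0.8 |
| 0.7 | 0.85 | 8% | 1.5 | 0.6 |

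Outside this range, ρ = 0.3 gives a ratio of 0.65 and a 3.5-point shift for d = 5. At ρ = 0.9 the ratio is 0.95 and the shift 0.5 points.

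**3. The gain and the shift trade off.** The variance ratio assumes that baseline is unrelated to conversion. With equal groups and a baseline difference of 0.5 SD, the variance of the adjusted contrast is inflated by 1 + 0.25 × 0.5² = 1.0625. The net ratio is then 0.70 × 1.0625 = 0.74 at ρ = 0.4, and 0.85 × 1.0625 = 0.90 at ρ = 0.7. At ρ = 0.9 it is 0.95 × 1.0625 = 1.01, so the gain is gone.

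**The case against.** The label in 11.4 includes ANCOVA, which implies a continuous covariate, and the SAP's habit elsewhere is to use baseline. The gap may therefore be an unnamed covariate rather than a decision to exclude it. That is fair, but the sentence lists its predictors and baseline is not among them. Followed as written, the model is unadjusted.

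A more substantial objection is that, for non-randomised groups, the change-score contrast and the baseline-adjusted contrast can answer different questions. If converters and non-converters have stably different levels, the raw difference in change may be the right description and adjustment may distort it. This stands. The shift in the working is a gap between two estimates, not a demonstrated bias, and it is a reason to show both.

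A reader might also infer three stronger things that the documents do not support:
- That the contrast behind the 100 subjects is itself analysed without baseline. The sizing concerns the anchor-based longitudinal validation, which belongs to the VAP. The VAP is not among the documents reviewed, and 11.4 does not designate any of its pairings as the sized test.
- That the study is underpowered. The stated power reproduces with the unadjusted ANOVA it names.
- That 11.4 carries the main evidence linking symptoms to conversion. SAP 7.2 makes it descriptive. In the primary objective (Protocol 10.5.2), PGI-S change defines the anchor and conversion is an additional one.

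**Conclusion.** The point holds for SAP 11.4 alone. As written, a comparison of groups formed after randomisation is not adjusted for a baseline score already collected, unlike the SAP's other ANCOVAs of PRO change.

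The size can be given only as a range, because neither the correlation nor any baseline difference is documented. With ρ of 0.4 to 0.7 and equal SDs, residual variance would be 70% to 85% of its unadjusted value. That is a best case, which assumes no relation between baseline and conversion. A hypothetical 5-point baseline difference would separate the two estimates by 3.0 to 1.5 points. Against the 7-point difference in the power statement and an SE of about 2.1 to 2.5 points, that is enough to change how a descriptive result reads. With ρ near 0.9, both the gain and the shift are small.

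Baseline adjustment would not make the contrast causal.

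**What to change.** In SAP 11.4, specify the ANCOVA as PRO change on conversion status and the baseline score of the same PRO, with treatment added in the overall analysis. Report the baseline-adjusted difference and its 95% CI beside the unadjusted difference and the point-biserial correlation, and keep all of them descriptive.

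Leave the sizing text in Protocol 10.1 and SAP 4.3.1 as it is. It reports a completed simulation tested by ANOVA, and renaming the test would misstate what was done.

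The cost is a short edit to 11.4 and one extra model per pairing, with no new data. The downside is a small loss of precision in the adjusted estimate if baseline is strongly imbalanced between converters and non-converters but only weakly related to change. Showing both estimates lets the reader see this.

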### **11.5. Intercurrent Event Assessment**

The assessment of ICEs is descriptive and will be performed to investigate the occurrence in the clinical trial setting.

The frequency and percentage of subjects experiencing each of the ICE types will be tabulated by treatment group.

In addition, the time to intercurrent event will be illustrated with Kaplan-Meier plot. Discontinuation of ALIS/ELC due to non-ICE reasons are considered censored and set to the date of last dose of ALIS/ELC.

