## 7.5. Intercurrent Events

The ICEs are defined as post-randomization events that occur after the study intervention has been initiated and which either precludes the observation of the outcome variable or affects its measurement or interpretation. This study identified ICEs as those leading to early ALIS/ELC therapy termination due to death, treatment (ALIS/ELC) related TEAE, use of rescue medication, or lack of efficacy.

When appropriate, efficacy analyses for secondary endpoints will be evaluated taking ICEs into consideration allowing a more precise estimation. Details on handling data after ICE occurred together with justification are provided in [Section 9](#).

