The missing data will be multiply imputed using PROC MI in SAS. Fifty replications are sufficient to reflect variability of the imputations. Logistic regression will be used in the MI procedure with model factors including randomization stratum (history of MAC lung infection, initial or subsequent) and randomized treatment group.

[REDACTED]

Imputations for subjects whose Month 6 conversion status is unavailable and who discontinued ALIS/ELC early due to a non-ICE event:

For subjects not experiencing ICE, their missing Month 6 conversion status will be imputed based on the observed data distribution (flagged as Ref\_MAR) from the subjects who completed 6 months of randomized therapy, have Month 6 conversion status available, and are randomized to the same treatment group. This approach is consistent with MAR approach.

The missing data will be multiply imputed using PROC MI in SAS. Fifty replications are sufficient to reflect variability of the imputations. Logistic regression

will be used in the MI procedure with model factor randomization stratum (history of MAC lung infection, initial or subsequent).

Imputations for subjects completing randomized therapy and whose conversion status at Month 6 is unavailable

Data for subjects who complete 6 months of the randomized treatment however Month 6 conversion status is not available will be imputed based on the observed distribution from the subjects who completed 6 months of randomized treatment, have Month 6 conversion status available, and were randomized to the same treatment group. This approach is consistent with MAR approach imputation. The missing data will be multiply imputed using PROC MI in SAS as described above.

Analysis methods

Following each round of imputation, a full set of subject's conversion status at Month 6 will be created by combining the observed values and sets of imputed values under the MNAR and MAR assumptions. This process will result in a total of 50 full sets.

The analysis as specified in Section 9.3.1.2 will be performed using each of the 50 full sets. The 50 sets of results will be then combined using Rubin's rule implemented via SAS PROC MIANALYZE with the specification of their effect estimates together with the corresponding standard errors, resulting in a single set of estimates and testing statistics for the treatment effect.

Imputation of conversion status by Month 7

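### SAP 11.5 censors non-ICE ALIS/ELC stops in the Kaplan-Meier plot of time to intercurrent event, although such a stop is a competing event, so the curve can overstate how many subjects have an ICE

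*SAP*

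**What the plan says.** SAP 7.5 limits ICEs to "those leading to early ALIS/ELC therapy termination due to death, treatment (ALIS/ELC) related TEAE, use of rescue medication, or lack of efficacy". SAP 9.3.2.2.1 repeats the same four reasons.

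SAP 11.5 describes how often ICEs occur under trial conditions and labels the assessment descriptive. It plans two displays:

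- A table: "The frequency and percentage of subjects experiencing each of the ICE types will be tabulated by treatment group".
- A plot: "the time to intercurrent event will be illustrated with Kaplan-Meier plot", with the censoring rule "Discontinuation of ALIS/ELC due to non-ICE reasons are considered censored and set to the date of last dose of ALIS/ELC".

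The section does not say how subjects who complete ALIS/ELC are censored, and it lists no any-ICE total. Neither document mentions a cumulative incidence function or another competing-risk method, and SAP Table 9 (changes to protocol-specified analyses) does not touch the point.

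Non-ICE stops are foreseen. SAP Appendix I has a separate imputation group, under culture conversion, for subjects "who discontinued ALIS/ELC early due to a non-ICE event". SAP 8.5 reports treatment discontinuation related to COVID-19.

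**The concern.** Kaplan-Meier censoring assumes that a censored subject could still have the event later, at the same rate as those who remain under observation. On the SAP's definition this cannot be so here. Once ALIS/ELC has been stopped for a non-ICE reason, nothing that follows can lead to its early termination, not even later rescue therapy or death.

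Read as a cumulative proportion, 1 minus Kaplan-Meier then describes a hypothetical setting in which nobody stops ALIS/ELC for other reasons, and does so only if those stops are unrelated to ICE risk. That independence is doubtful. Whether a stop for an adverse event counts as an ICE turns on the investigator's related/not related judgement (protocol 9.9.5).

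Two things are at stake. The plot may end above the crude proportion of subjects with an ICE, although the section sets out to describe actual occurrence. The visual comparison of ALIS with ELC may also be distorted if ICE rates, non-ICE stop rates or their timing differ between arms.

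**Working it through.** **Inputs from the documents.** 100 subjects, 50 per arm (SAP 4.3.1); 6 months of treatment (SAP 4.2); the ICE definition (SAP 7.5); the estimator and censoring rule (SAP 11.5).

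**Inputs assumed.** Neither document gives an ICE rate or a non-ICE stop rate, so there is no planned figure to reproduce. I let the true Month 6 proportion with an ICE, *a*, run from 10% to 30%, and the proportion with a non-ICE stop, *b*, from 0% to 30%. The missing-data conditions in the SAP 4.3.1 power simulation also run from 0% to 30%. They are only a loose guide, because they are not discontinuation rates.

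**Formula.** With constant cause-specific hazards over 6 months and everyone followed to an ICE, a non-ICE stop or Month 6:

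- total cumulative hazard H = −ln(1 − a − b)
- ICE share of it = H × a/(a + b)
- 1 − KM at Month 6 = 1 − exp(−H × a/(a + b))

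**Worked case.** For a = 20% and b = 15%: H = −ln(0.65) = 0.431; ICE share = 0.431 × 0.20/0.35 = 0.246; 1 − KM = 1 − exp(−0.246) = 21.8%. The excess over the true 20% is 1.8 points.

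**Value of 1 − KM at Month 6:**

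| True ICE | b = 0% | b = 5% | b = 10% | b = 20% | b = 30% |
|---|---|---|---|---|---|
| 10% | 10.0% | 10.3% | 10.6% | 11.2% | 12.0% |
| 20% | 20.0% | 20.6% | 21.2% | 22.5% | 24.2% |
| 30% | 30.0% | 30.9% | 31.8% | 34.0% | 36.8% |

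At a = 25% and b = 30% the value is 30.4%, an excess of 5.4 points.

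**Against sampling error.** The standard error of 1 − KM was taken from 4,000 simulated arms of 50 subjects:

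| a / b | Excess (points) | SE (points) | Excess / SE |
|---|---|---|---|
| 20% / 15% | 1.8 | 6.1 | 0.30 |
| 20% / 20% | 2.5 | 6.3 | 0.40 |
| 30% / 20% | 4.0 | 7.1 | 0.57 |
| 20% / 30% | 4.2 | 6.8 | 0.62 |
| 25% / 30% | 5.4 | 7.4 | 0.74 |
| 30% / 30% | 6.8 | 7.8 | 0.87 |

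**Timing.** Take one arm of 50 with 10 ICEs and 5 non-ICE stops; the crude proportion is 10/50 = 20.0%. If all 5 stops come before the ICEs, 1 − KM = 10/45 = 22.2%. If all 5 come after, 1 − KM = 20.0% and there is no gap.

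**Direction.** With follow-up otherwise complete, 1 − KM cannot fall below the crude percentage. In simulated arms of 50 it exceeded the crude percentage in 85% (a = 10%, b = 5%), 90% (20%, 5%), 99% (20%, 10%) and 100% (20%, 20%).

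**After the fix.** The Aalen-Johansen estimate with non-ICE stops as a competing event equalled the crude any-ICE percentage in every simulated arm. At a = 20% and b = 10% the simulation means were 20.0% for Aalen-Johansen, 20.0% crude and 21.2% for 1 − KM.

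**The case against.** The strongest reply is that the real-world quantity is already reported. SAP 11.5 tabulates each ICE type by arm before it adds the plot, and SAP 8.1 tabulates discontinuations with reasons. Kaplan-Meier with cause-specific censoring is a legitimate display of the ICE hazard among subjects still on ALIS/ELC, and nothing says the curve will be quoted as a proportion. The shift is below one standard error in every scenario tried, and the larger values need non-ICE stop rates of 20-30%, for which no document gives support. SAP 7.2 disclaims inference.

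Most of this stands, and it fixes the weight of the point. It does not remove the point. SAP 11.5 does not label the curve as a net or cause-specific quantity, and the section's aim is actual occurrence, which this curve does not estimate once non-ICE stops precede ICEs.

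Three stronger readings are tempting, and the documents do not support them:

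- *The curve will necessarily overstate and disagree with the table.* It does so only if at least one non-ICE stop comes before an ICE. Also, the planned table is by ICE type, so there is no tabulated any-ICE figure for the curve to disagree with until that total is added.
- *The arm with more non-ICE stops has the larger excess.* That holds only at equal ICE rate and timing. At a = 10% and b = 30% the excess is 2.0 points; at a = 30% and b = 20% it is 4.0 points, so the arm with fewer non-ICE stops has the larger excess.
- *The efficacy results are affected.* The imputation rules in SAP 9.3.1.2.1, 9.3.2.2.1 and Appendix I use each subject's ICE status, not this curve.

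**Conclusion.** The point holds as a minor reporting error. On the SAP's own definition a non-ICE stop of ALIS/ELC precludes an ICE, and censoring it makes 1 minus Kaplan-Meier too high as a cumulative proportion whenever such a stop precedes an ICE. The bias runs in one direction only.

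Its size rests wholly on assumed rates and constant hazards. It is about 0.3 to 2.5 points for ICE rates of 10-20% with non-ICE stops of 5-20%, about 4 to 7 points in the combinations from 20%/30% and 30%/20% up to 30%/30% (ICE/non-ICE), and nil without non-ICE stops. The arm comparison can be distorted in either direction, depending on ICE rates, non-ICE stop rates and timing in each arm. No endpoint, test or imputation changes.

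**What to change.** In SAP 11.5:

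- Replace the Kaplan-Meier plot with Aalen-Johansen cumulative incidence curves by arm for any ICE, with ALIS/ELC discontinuation for a non-ICE reason as the competing event, also plotted.
- State that subjects who complete ALIS/ELC are censored at their last dose.
- Add an any-ICE row and a non-ICE-stop row to the ICE table. The curves can then be checked against it; with only the per-type rows they would not end at any tabulated figure.

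If the sponsor prefers to keep a Kaplan-Meier curve, it should be labelled as a cause-specific (net) quantity and not read as the proportion with an ICE.

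The cost is one changed figure in standard software (for example PROC LIFETEST with an event code) and two table rows. No new data are needed and no other analysis changes.
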